## 9.3 Exploratory Efficacy Analyses

The virologic efficacy of Brensocatib will be evaluated.

- 1. The percentage of participants with SARS-CoV-2 detectable in nasopharyngeal (NP) sample (in hospital, Tayside only)
- 2. Quantitative SARS-CoV-2 virus in NP samples (Tayside only)
- 3. \*Neutrophil elastase and heparin binding protein measurement in blood (in hospital, Tayside only)
- 4. \*Neutrophil functional studies (NET formation, phagocytosis, elastase release, neutrophil proteomics- (Tayside and Sheffield only)

\*These analysis will be omitted in circumstances where there is no laboratory availability to process the samples in time, it is not possible to carry out analysis on stored samples.

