2. RATIONALE

Neutrophil elastase, proteinase-3 and cathepsin-G are activated during neutrophil maturation in the bone marrow through dipeptidyl peptidase 1 (DPP1; also known as cathepsin C), which removes the N-terminal dipeptide sequence of neutrophil serine proteases allowing active enzymes to be packaged into granules prior to release of neutrophils into the circulation.⁴ Brensocatib (INS1007, formerly AZD7986) is an orally delivered selective, competitive, and reversible inhibitor of DPP1. Brensocatib has been shown to inhibit neutrophil serine protease activity in blood in both animal models and healthy volunteers.⁴

We recently conducted a large phase 2 study of Brensocatib in patients with bronchiectasis designed to test if treatment with Brensocatib could reduce infective exacerbations and reduce neutrophil elastase activity in the lung in bronchiectasis patients. The study met its primary endpoint of time to first exacerbation and key secondary endpoint of the frequency of exacerbations as well as showing marked reductions in neutrophil elastase concentrations in sputum. Due to the need to replace the circulating pool of neutrophils with new neutrophils which are deficient in elastase, Brensocatib does not have its effect immediately, but rather over several days. Elastase concentrations were reduced at the first time point at day 14 in the phase 2 study, with very large reductions observed at the second time point at day 28.

proposed below. We hypothesise that the mechanism of action of Brensocatib to reduce protease activity will be more rapid in COVID-19 patients compared to bronchiectasis due to a more rapid turnover of neutrophils in acute illness. The objective is to test whether by reducing neutrophil protease activity in neutrophils we can prevent or reverse the development of ARDS and thereby improve outcomes in individuals with COVID-19 infection.

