7.12. Storage and analysis of clinical samples

Storage and analysis of samples will only occur at the Tayside and Sheffield sites. The anonymisation, processing and storing of these specimens will be detailed in a local Laboratory Manual.

Sheffield:

- Will collect blood samples as per Schedule of Procedures, Appendix 4.
- Neutrophil function studies will be carried out at the Sheffield site.
- Blood will be processed and stored at Sheffield for later transfer to the Tayside laboratory for further analysis. Excess may be stored in the Tayside laboratory for future research use after trial results have been obtained.

Tayside:

- Will collect blood, sputum, endo-tracheal and nasal swab samples as per Schedule of Procedures, Appendix 4.
- Will carry out analysis as per exploratory end points.
- Preparations of blood, sputum and nasal swabs may be stored for future research use after trial results have been obtained.
- Excess biological samples that are being taken for clinical reasons may be stored for future use if no longer required for clinical purposes

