⁺Excess biological samples that are being taken for clinical reasons may be stored for future use if no longer required for clinical purposes (Tayside only).

^a For those participants who are intubated.

[∞]These assessments will not be completed if the participant has been discharged from hospital.

^b For the Tayside and Sheffield site only, the day 29 assessments will be carried out face-to-face either at a NHS facility or at the participant's home. Home visits will only be carried out if no one in the household has symptoms of COVID-19.

^cResearch blood samples (Tayside and Sheffield only) and, once discharged, assessments may be completed within +/- 1 day

^dScreening and randomisation may occur on the same day if all eligibility criteria are met. Day of first dose of IMP will be considered as day 1 for the calculation of follow up assessments.

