or blood) If Applicable	^							
Record Adverse Events		X	X	X	X	X	X	X
Randomisation		X						
Dispense Trial Drugs		X						
Drug Return And							Х	
Compliance Check							^	

^ Vital Signs: Blood Pressure, pulse, temperature, oxygen saturation

\*indicates procedures that will be performed by the clinical team as part of routine care but results will be recorded and included in the eCRF.

If not performed by the clinical team, but clinically indicated, the research team may assist in this being performed but all processes will avoid duplication and exposure to potentially infected participants.

+Excess biological samples that are being taken for clinical reasons may be stored for future use if no longer required for clinical purposes (Tayside only).

<sup>a For those participants who are intubated.

∞These assessments will not be completed if the participant has been discharged from hospital.

<sup>b For the Tayside and Sheffield site only, the day 29 assessments will be carried out face-to-face either at a NHS facility or at the participant's home. Home visits will only be carried out if no one in the household has symptoms of COVID-19.

 $^{c}$ Research blood samples (Tayside and Sheffield only) and, once discharged, assessments may be completed within +/-1 day

dScreening and randomisation may occur on the same day if all eligibility criteria are met. Day of first dose of IMP will be considered as day 1 for the calculation of follow up assessments.

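### SAP 9.3 limits blood elastase and viral detection to inpatients, but the schedule also takes the day-29 samples from discharged participants

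*SAP*

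**What the plan says.** SAP 9.3 lists four exploratory items. Two carry an in-hospital limit: item 1, "The percentage of participants with SARS-CoV-2 detectable in nasopharyngeal (NP) sample (in hospital, Tayside only", and item 3, "Neutrophil elastase and heparin binding protein measurement in blood (in hospital, Tayside only". Two do not: item 2, "Quantitative SARS-CoV-2 virus in NP samples (Tayside only", and item 4, "Neutrophil functional studies (NET formation, phagocytosis, elastase release, neutrophil proteomics- (Tayside and Sheffield only". Protocol 3.7 has the same in-hospital label for viral detection. Its elastase row is incomplete in the text available for this review. SAP 7.6 lists blood elastase by treatment arm in the preliminary analysis, with no limit by site or hospital status.

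The schedule (protocol 16.4, repeated as SAP Table 1) uses an infinity mark whose footnote reads "These assessments will not be completed if the participant has been discharged from hospital". Research blood (Tayside and Sheffield) has the mark at days 8 and 15, and the nasal swab (Tayside) has it at day 15. Neither has it at day 29. Another footnote states "For the Tayside and Sheffield site only, the day 29 assessments will be carried out face-to-face", at a health-service facility or at home, and protocol 7.2 pays travel expenses for that visit.

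On Sheffield samples, protocol 7.12 says "Blood will be processed and stored at Sheffield for later transfer to the Tayside laboratory for further analysis". The footnote to SAP 9.3 items 3 and 4 says these analyses are left out when no laboratory can process samples in time, because stored samples cannot be analysed.

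**The concern.** The schedule sets out to collect day-29 blood and swabs from people who have gone home. Taken at face value, the SAP label excludes those results from items 1 and 3. Being in hospital at day 29 is part of the primary ordinal outcome, so an inpatient-only comparison at that visit conditions on something the treatment is meant to change. If brensocatib works, fewer of its participants remain, and they are selected differently from those remaining on placebo.

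A null day-29 elastase result in such a subset could mean that the drug did not lower its target, or only that the samples were few and selected. Because items 2 and 4 and SAP 7.6 have no such limit, two analysts could also follow the SAP in good faith and report different elastase results.

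**Working it through.** **Step 1. The passages side by side.**

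| Place | Measurement | Sites | Limited to inpatients? |
|---|---|---|---|
| SAP 9.3 item 1 | Percent with detectable virus | Tayside | Yes |
| SAP 9.3 item 2 | Quantitative virus | Tayside | No |
| SAP 9.3 item 3 | Blood elastase, heparin binding protein | Tayside | Yes |
| SAP 9.3 item 4 | Functional studies, including elastase release | Tayside, Sheffield | No |
| SAP 7.6 | Blood elastase by arm | Not stated | No |
| Schedule | Research blood | Tayside, Sheffield | Days 8 and 15 yes; day 29 no |
| Schedule | Nasal swab | Tayside | Day 15 yes; day 29 no |

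Only the day-29 results of discharged participants are in dispute.

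**Step 2. Does the planning distribution reproduce the plan's own figures?** Inputs are the placebo percentages in protocol Table 4: death 2, ventilation or ECMO 1, non-invasive ventilation or high flow 2, oxygen 7, hospitalised without oxygen 8, discharged with limitation 38, discharged without limitation 42. The Whitehead formula for 1:1 allocation is N = 12(z_α/2 + z_β)² / [(ln OR)²(1 − Σp̄³)], where p̄ is the mean of the two arms' proportions. With two-sided 5% and 85% power it gives 409.5 at OR 1.75 (stated 412) and 269.7 at OR 2 (stated 272). Power for 400 participants at OR 1.75 is 84.2% (stated about 85%). The distribution can therefore be used as the plan uses it.

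**Step 3. Share alive and in hospital.**
- Placebo: 1 + 2 + 7 + 8 = 18%.
- Brensocatib, OR 1.75, hospitalised or dead: odds 0.20/0.80 = 0.25; 0.25/1.75 = 0.1429; probability 0.1429/1.1429 = 12.5%.
- Brensocatib, dead: odds 0.02/0.98 = 0.02041; divided by 1.75 = 0.01166; probability 1.15%.
- Brensocatib, alive in hospital: 12.5 − 1.15 = 11.35%. At OR 2 it is 10.1%.
- Share of survivors lost to an inpatient limit: placebo 80/98 = 82%; brensocatib 87.5/98.85 = 89%.

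**Step 4. Precision at day 29.** Per 100 randomised per arm (the ratio does not depend on this number) and with equal variances assumed:
- All survivors sampled: √[(1/18 + 1/11.35)/(1/98 + 1/98.85)] = √(0.1437/0.0203) = 2.66.
- If only half the discharged are sampled (assumption), the sets are 18 + 40 = 58 and 11.35 + 43.75 = 55.1: √[0.1437/(1/58 + 1/55.1)] = √(0.1437/0.0354) = 2.0.

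**Step 5. Illustration in counts.** The documents give neither the Tayside number nor an elastase standard deviation, so both are assumed here: Tayside totals of 40, 80 and 160, and a difference of 0.8 SD. Power is Φ(0.8/√(1/n₁ + 1/n₂) − 1.96), at OR 1.75.

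| Assumed Tayside N | Inpatients at day 29 | Power | Survivors at day 29 | Power |
|---|---|---|---|---|
| 40 | about 6 | 16% | about 39 | 71% |
| 80 | about 12 | 27% | about 79 | 94% |
| 160 | about 23 | 47% | about 157 | >99% |

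**The case against.** **The label may describe where samples are taken.** SAP 9.3 gives no time point, test or analysis set, so it does not state outright that samples are discarded. This stands as a caution, and the loss is therefore conditional on the reading. But a sampling-location reading does not fit a day-29 visit held at a facility or at home, so the text needs correcting either way.

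**A reader might infer that the whole test of mechanism rests on a small selected remnant, or that blood elastase is the only check on target engagement.** The documents do not support either. Item 4 includes elastase release at two sites without an in-hospital limit, and SAP 7.6 has no limit. At days 8 and 15 the schedule, not SAP 9.3, confines sampling to inpatients, and no in-hospital share is given for day 8.

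**A reader might also infer that day 29 is the most informative time.** Protocol section 2 does report reductions "with very large reductions observed at the second time point at day 28", but these were in sputum in bronchiectasis, and the same section expects a faster effect in COVID-19. Day 29 is the last scheduled sample; the documents do not show that it is the best one.

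**The size in step 4 is an upper contrast.** Home visits require a household free of symptoms, and protocol 7.8 takes swabs only where practical. Samples are scheduled, not guaranteed. This stands, and the half-sampled case allows for it.

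**Adding Sheffield blood may not be feasible.** The stored-sample footnote speaks against it. This also stands and limits the fix.

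**Conclusion.** The inconsistency is real and confined to day 29. If the in-hospital label defines the analysis set for items 1 and 3, it removes scheduled results from discharged participants and leaves about 18% of placebo and 11% of brensocatib participants (10% at OR 2), selected on a component of the primary outcome. The standard error would be up to about 2.7 times larger, or about twice as large if half of those discharged are sampled.

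These figures rest on the planning distribution, on proportional odds and on equal variance in inpatients and discharged participants. The protocol text dates that distribution to day 29, but the title of its Table 6 says day 15. If day 15 is right, the day-29 inpatient share is probably smaller still. The direction of any selection bias cannot be worked out from the documents.

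The analyses are exploratory, at one or two sites, and the primary result does not depend on them. The change is worth making because it is cheap and settles which elastase result will be reported.

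**What to change.** - In SAP 9.3 items 1 and 3, and in protocol 3.7 where the label appears for viral detection, remove the in-hospital restriction for day 29.
- State the time points, analysis set and method. At day 29 analyse every participant sampled, adjusting elastase for the value taken at randomisation.
- Report days 8 and 15 (day 15 for the swab) as inpatient-only, with the number sampled in each arm.
- Use the same set for the elastase comparison in SAP 7.6.
- Reconcile protocol 7.12, which stores Sheffield blood for later transfer, with the SAP 9.3 footnote on stored samples. Include Sheffield blood in the elastase analysis only once that is settled.

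The cost is some additional assays on samples already scheduled, plus a matching change to the protocol wording. No new visit or sample is needed.

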## 10 Safety Analyses

Safety endpoints include cumulative incidence of SAEs, discontinuation or temporary suspension of treatment, changes in white cell count, haemoglobin, platelets, creatinine, total bilirubin, ALT and AST over time. Adverse events of special interest; hyperkeratosis (skin), infection, and dental complications will be reported. These events will be analysed univariately. The proportion of participants who had adverse events will compared between both the groups using Poisson regression. Adverse events leading to premature discontinuation from the study intervention and serious AEs will be presented either in a table or a listing.

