7.8. Trial assessments

Trial assessments will be performed according to the Schedule of Procedures, Appendix 4.

After informed consent, the following assessments will be reviewed to determine eligibility requirements as specified in the inclusion and exclusion criteria:

- Focused medical history, taken from medical records, including the following information:
 - Approximate day of onset of COVID-19 symptoms
 - History of chronic medical conditions related to inclusion and exclusion criteria
 - o Medication allergies
 - Review medications and therapies for this current illness
- Review recent radiographic imaging (x-ray or CT scan)
- Physical examination findings
- SpO₂ on air
- Obtain blood for screening laboratory evaluations if not done in the preceding 72 hours:
 - ALT
 - AST
 - o Creatinine
 - o eGFR
 - Lymphocyte count

Clinical screening laboratory evaluations will be performed locally by the site laboratory. The overall eligibility of the participant to participate in the trial will be assessed once all screening values are available. The screening process can be suspended prior to complete assessment at any time if exclusions are identified by the trial staff. Equally, if a patient qualifies for participation based on one inclusion criteria of severe, e.g requirement for supplemental oxygen, it is not necessary to perform a physical examination to confirm the presence of rales or crackles as the patient is already eligible. Trial participants who qualify will be immediately randomized.

It is likely that the above assessments to confirm eligibility will be carried out by the clinical team during routine care of patients being assess for COVID-19. Where these assessments have been carried out by the clinical team in the preceding 72 hours, the most recent of these results will be used to prevent duplication and further exposure of the trial staff to patients with COVID-19. If any screening procedures have not been carried out in the previous 72 hours (96 hour for positive SARS-CoV-2 test) hours for these will be completed by the trial staff. Screening procedures will only be recorded/carried out after consent.

For all baseline assessments and follow-up assessments, refer to Schedule of Procedures for procedures to be done, and details below for each assessment.

Clinical Assessments

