## 10.5 Clinical Laboratory Evaluations

Clinical safety laboratory adverse events are collected Day 0/1, 3, 5, 8, 11 and Day 15 and 29 if able to return to clinic or still hospitalized. Parameters evaluated include white blood cell count, platelet, haemoglobin concentration, creatinine, total bilirubin, ALT and AST. Laboratory safety parameters will be graded according to the Division of AIDS (DAIDS) Table for Grading the Severity of Adult and Pediatric Adverse Events, version 2.1 (July 2017). The distribution of Grade 3 and 4 chemistry and haematology laboratory results by time point and treatment group will be presented.

Descriptive statistics including mean, median, standard deviation, maximum, and minimum values and change from baseline by time point, for all and each chemistry and haematology laboratory parameter will be summarized by treatment arm.

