## Oxygenation

No of days free from oxygen

Duration of new oxygen use

Mechanical ventilation

Number of patients receiving new mechanical ventilation

No of days free from ventilation

Duration of new ventilation used

Duration of hospital stay - days

28-day mortality

Table 10: Safety analyses

	Brensocatib N =	Placebo N =	Effect estimate (95% CI)
% of patients with at least 1 AE			
Incidence of SAEs			
Discontinuation or temporary suspension of treatment			
Changes in white cell count			
Changes in haemoglobin			
Changes in platelets			
Changes in creatinine			
Changes in total bilirubin			
Changes in ALT			
Changes in AST			
Adverse events, n (%):			
Hyperkeratosis (Skin)			
Infections			
Dental complications			

Table 11: Adverse Events

Adverse Event - n (%)	Brensocatib	Placebo
	N =	N =
Death		
Life-threatening		
Required hospitalisation		
Resulted in persistent or significant disability		
Medically significant		
Total		

Table 12: Summary of all adverse events - System Organ Class Level

N = N =	Total	Placebo	Brensocatib
	N=	N =	N =

Number of participants

Number of participants with adverse events

Number of participants without adverse events

Number of adverse events

Cardiac disorders

Eye disorders

Gastrointestinal disorders

General disorders and administration site conditions

Infections and infestations

Injury, poisoning and procedural complications

Investigations

Metabolism and nutrition disorders

Musculoskeletal and connective

tissue disorders

Nervous system disorders

No Code

Psychiatric disorders

Renal and urinary disorders

Respiratory, thoracic and mediastinal disorders

Skin and subcutaneous tissue

disorders

Vascular disorders

Table 13: Summary of all adverse events - Preferred Term Level

Brensocatib	Placebo	Total
N =	N =	N=

Number of participants

Number of participants with adverse

events

Number of participants without adverse

events

Number of adverse events

Abdominal discomfort

Abdominal pain

Acute kidney injury

Arthralgia

Back pain

Blood glucose increased

Bradycardia

Cerebrovascular accident

Chest discomfort

Chest pain

Clostridium difficile infection

Constipation

Cough

Delirium

Diarrhoea

Dizziness

Drug eruption

Dry mouth

Dry skin

Dysarthria

Dyspepsia

Dyspnoea

Dysuria

Electrocardiogram abnormal

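### SAP Table 10 asks for effect estimates on seven laboratory changes but names no model; adding the baseline value as a covariate would narrow the intervals at almost no cost

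*SAP*

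**What the plan says.** SAP 10 lists among the safety endpoints "changes in white cell count, haemoglobin, platelets, creatinine, total bilirubin, ALT and AST over time". It then names the adverse events of special interest (hyperkeratosis, infection, dental complications) and continues: "These events will be analysed univariately".

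SAP 10.5 sets out the laboratory reporting. Collection is described as "Clinical safety laboratory adverse events are collected Day 0/1, 3, 5, 8, 11 and Day 15 and 29". The summary is descriptive statistics, with "change from baseline by time point, for all and each chemistry and haematology laboratory parameter will be summarized by treatment arm". For graded results, "The distribution of Grade 3 and 4 chemistry and haematology laboratory results by time point and treatment group will be presented".

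SAP section 16, Table 10, has one row per parameter, for example "Changes in creatinine", next to a column headed "Effect estimate (95% CI" and closing bracket. No section says how those seven estimates are obtained: model, covariates, scale and day are all unstated. Elsewhere the SAP is more specific. Sections 9.1, 9.2.1 and 9.2.4 adjust for age and site, and 11.1 names a mixed model.

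Baseline values should exist. The Schedule of Procedures (Protocol Appendix 4, repeated as SAP Table 1) marks full blood count, urea and electrolytes, and liver function tests at screening. Protocol 7.8 adds: "Obtain blood for screening laboratory evaluations if not done in the preceding 72 hours".

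**The concern.** A table shell that demands an effect estimate and interval commits the trial to a between-arm comparison, not just a descriptive summary. With only change from baseline described, the default is likely to be a plain difference in mean change. That leaves available precision unused, and it leaves the method for seven safety estimates open until the data are in hand.

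The laboratory endpoints carry some weight. Protocol 9.2 keeps deterioration in renal or liver function and changes in blood count out of adverse event recording, because they are recorded as safety endpoints instead. Intervals wider than they need to be make it harder both to detect a laboratory effect and to exclude one.

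A second, smaller matter is the graded results. Marginal counts of Grade 3 and 4 at each time point do not show whether a high grade on, say, day 8 is new or was already present at entry in the same participant.

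**Working it through.** **What the plan gives.** The documents contain no SD, correlation, precision or power figure for laboratory safety, so there is no stated figure to reproduce. The sample size tables concern the primary outcome and do not bear on this point. The inputs taken from the documents are 400 participants (SAP 5.1) and 1:1 allocation (SAP 5.3), so about 200 per arm at most. Follow-up values exist only where blood was taken for clinical care (Protocol 7.8), so the number tested will be lower. The correlation rho between baseline and follow-up is an assumption, shown as a range.

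**Step 1: variances.** Take a common SD s at both times. The variance per participant is:
- change from baseline: 2s²(1 − rho)
- baseline-adjusted (ANCOVA): s²(1 − rho²)

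The variance ratio, change to ANCOVA, is 2/(1 + rho), so the interval-width ratio is sqrt(2/(1 + rho)). It does not depend on the number tested.

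**Step 2: numbers.** The 95% half-width in SD units with 200 per arm is 1.96 × sqrt(2/200) = 0.196, multiplied by sqrt(2(1 − rho)) for change or sqrt(1 − rho²) for ANCOVA.

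| rho (assumed) | Change | ANCOVA | Excess width | (1+rho)/2 |
|---|---|---|---|---|
| 0.3 | 0.232 | 0.187 | 24% | 0.65 |
| 0.5 | 0.196 | 0.170 | 15% | 0.75 |
| 0.7 | 0.152 | 0.140 | 8% | 0.85 |
| 0.8 | 0.124 | 0.118 | 5% | 0.90 |
| 0.9 | 0.088 | 0.085 | 3% | 0.95 |

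The last column is the fraction of participants that ANCOVA would need to match the precision of the change score.

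**Step 3: is equal variance essential?** No. With SDs s0 at baseline and s1 at follow-up, the change variance minus the ANCOVA variance is (s1² + s0² − 2 rho s0 s1) − s1²(1 − rho²) = (s0 − rho s1)². This is never negative, so adjustment does not lose precision in this comparison. Only the size of the gain varies.

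**Step 4: bias or precision?** A simulation with no true effect (200 per arm, 4,000 runs) gave mean arm differences within 0.002 SD of zero for both methods. The ratio of their standard errors was 1.24, 1.17 and 1.05 at rho 0.3, 0.5 and 0.8, in line with the formula. The issue is precision only.

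**Step 5: scale.** Creatinine, bilirubin, ALT and AST are usually right-skewed. As an illustration for ALT, assume log SD 0.7, a true 25% rise and 100 tested per arm (3,000 runs). Power was:

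| rho | Raw change | Raw ANCOVA | Log change | Log ANCOVA |
|---|---|---|---|---|
| 0.4 | 44% | 56% | 53% | 68% |
| 0.6 | 59% | 67% | 69% | 81% |

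Both the covariate and the log scale contribute. At rho 0.8 the covariate alone on the raw scale moves power only from 85% to 87%, and at 0.9 both are 99%.

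**The case against.** **Baseline is already used.** A reader might infer that the plan ignores the entry value, so that abnormality present at entry counts as arising on drug. The documents do not support this for the mean changes: SAP 10.5 specifies change from baseline, so each participant's entry value is subtracted. What is missing is baseline as a covariate.

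**The univariate sentence may not reach the laboratory data.** This objection stands. The sentence speaks of events and directly follows the adverse events of special interest. The plan is better read as silent on the laboratory model than as choosing to leave baseline out. Table 10 still needs a method.

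**Nothing is biased.** Also correct. Under randomisation the change score is unbiased, and a wider interval does not move an estimate towards no difference.

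**The graded results are only presented.** SAP 10.5 plans a distribution, with no ratio or test. Suppose 4% per arm enter with a persisting Grade 3 or 4 value, and new cases arise in 3% v 7.5% of the rest. The totals are 0.04 + 0.96 × 0.03 = 6.9% and 0.04 + 0.96 × 0.075 = 11.2%. Their ratio, about 1.6, is below the true 2.5, but it is not a planned output, and the difference of 4.3 points is the same with or without the persisting cases. Day 0/1 is a collection day, so entry grades should be visible by arm, and entry limits on ALT/AST, eGFR and neutrophils restrict some of them. What remains is that marginal counts cannot show persistence within a participant.

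**Other evidence exists.** The DMC reviews laboratory data (Protocol 2.1), and the SAP adverse event shells list acute kidney injury, abnormal liver function test and increased transaminases. The laboratory estimates are therefore not the only view of these effects.

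**Baseline coverage.** The screening list in Protocol 7.8 names only ALT, AST, creatinine, eGFR and lymphocytes. Bilirubin is not named there or in the follow-up list. The case for a baseline on all seven parameters rests on the panels in the Schedule of Procedures.

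**Conclusion.** The point holds as a matter of precision and specification. Table 10 asks for seven effect estimates without a stated method. If they are computed as unadjusted change scores, their intervals are 24% wider than baseline-adjusted ones at rho 0.3, falling to 3% at rho 0.9. The size rests on correlations that the documents do not give, and on equal variances at the two times. The gain is material at low to moderate correlation and small at high correlation. The further gain from the log scale rests on the usual skew of four of the analytes and on the illustrative ALT inputs.

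The lack of a shift table for graded results is a secondary reporting gap. It is not evidence that the planned tabulation misstates a treatment effect.

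**What to change.** In SAP 10 and 10.5, state that each laboratory effect in Table 10 is estimated by regressing the post-baseline value on arm and the participant's baseline value, with the age stratum and site used elsewhere in the SAP. Analyse creatinine, bilirubin, ALT and AST on the log scale and report ratios. Name the day or days to which each Table 10 row refers, and limit the univariate sentence to the adverse events it is meant for. If only one change is made, add the baseline covariate.

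A full repeated-measures model with arm-by-day terms and several random effects is not needed for this gain. It would also be debatable, because later values come only from inpatients tested for clinical reasons.

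Add a baseline-to-worst-grade shift table by arm beside the Grade 3 and 4 tabulation.

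The cost is a few sentences in the SAP, one table shell and minor programming. No new data are required.
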